## 7.9.2 Primary Safety Endpoint

The primary safety endpoint of this study will be the incidence of composite Major Adverse Events (MAE) at 30 days following stenting of an obstruction in the iliofemoral venous segment. MAEs will be adjudicated by a Clinical Events Committee (CEC), except for stent thrombosis and stent migration as they are confirmed by core laboratory.

The components of the 30-day MAE composite include:

- All-cause death occurring post-procedure
- Clinically significant (i.e. symptomatic, confirmed by CT pulmonary angiography) pulmonary embolism
- Major bleeding complication (procedural)
- Stent thrombosis confirmed by imaging as assessed by core laboratory
- Stent migration confirmed by imaging as assessed by core laboratory

Note: Migration excludes stent dislodgement at the index procedure as may occur with under-sizing of a stent.

More details of the reporting rules are used to determine this endpoint can be found in section 10.3.1.

### 7.9.2.1 Hypothesis Testing

The review of the literature that provided results on the composite MAE endpoint components suggests an expected rate of 5.6% (see ABRE CIP Appendix A Scientific Literature Search). It should be noted that considerably less data, compared to primary patency, was found for the components of this composite endpoint.

Therefore, due to the greater uncertainty, a relatively larger margin of indifference was used of 6.8% giving a performance goal of 12.5%. Formally, the null and alternative hypotheses to be tested appear below:

$$H_0: P \geq PG$$
$$H_A: P < PG$$

where P is the rate of the composite primary safety endpoint at 30 days in the study population and PG is the performance goal of 12.5%.

### 7.9.2.2 Statistical Method

The primary safety failure rate is calculated as the number of subjects who had a major adverse event within 30 days divided by the number of evaluable subjects who had enough follow up (at least 23 days for 30-day visit) plus any subjects who had a major adverse event within 30 days. Primary safety failure rate and the exact one-sided 97.5% upper confidence limit (UCL) will be reported. The primary safety objective will be met if the exact one-sided 97.5% UCL is below 12.5%.

For the primary safety endpoint, subjects will be included in the analysis and considered evaluable if:

- (a) the subject experiences at least one of the primary safety composite events within 30 days, or
- (b) stent migration and/or stent thrombosis within 30 days confirmed by imaging as assessed by core laboratory, or
- (c) the subject has at least 23 days of clinical follow up without an event in the primary safety endpoint.

Tiping point analysis for primary safety endpoint as sensitivity analysis is mentioned in section 7.4.2.

### 7.9.3 Secondary Endpoints

To assess how the subjects are doing clinically, the following secondary endpoints will be evaluated. All secondary endpoints will be evaluated using descriptive statistics. No inferential analyses are planned. Detailed analysis methods for core laboratory endpoints and endpoints assessed by office visits can be found in Section 10.

In addition, time-to-event analysis will be performed and Kaplan Meier (KM) estimates with two-sided 95% confidence interval using Peto formula will be reported for major adverse events (MAE) and its component events through 12 months, and annually through 36 months.

#### Acute success secondary endpoints

1. **Device success:** Successful delivery and deployment of the Abre stent in the target lesion with successful removal of the delivery system.
2. **Lesion success:** Venographic evidence of <50% final residual stenosis of the stented segment of the target lesion after post-dilation, when applicable, and as assessed by core laboratory.
3. **Procedure success:** Lesion success without procedure-related MAEs prior to hospital discharge within 30 days.

Note: If core laboratory is unable to assess the venographic evidence, site reported data will be used.

**Late success secondary endpoints**

- 4. Primary Assisted Patency at 12 months:** Uninterrupted patency of the stented segment of the target lesion with a secondary intervention, also known as an adjunctive treatment (e.g. balloon venoplasty, subsequent stenting, etc.).
- 5. Secondary Patency at 12 months:** Patency of the stented segment of the target lesion after subsequent intervention for an occlusion.
- 6. Target Lesion Revascularization (TLR) through 30 days, 6-, 12-, 24- and 36 months:** Any reintervention of the stented segment of the target lesion.
- 7. Major Adverse Events (MAE) through 6-, 12-, 24- and 36 months:** MAEs include:
  - All-cause death occurring post-procedure
  - Clinically significant (i.e. symptomatic, confirmed by CT pulmonary angiography) pulmonary embolism
  - Major bleeding complication (post-procedural)
  - Stent thrombosis confirmed by imaging as assessed by core laboratory
  - Stent migration confirmed by imaging as assessed by core laboratoryNote: Migration excludes stent dislodgement at the index procedure as may occur with undersizing of a stent  
All MAEs will be adjudicated by a CEC, except for stent thrombosis and stent migration as they are confirmed by core laboratory.
- 8. Delayed Stent Migration at 12-, 24-, and 36 months:** position change of a venous stent observed with an imaging modality > 1 cm from its original location at the conclusion of the index procedure, as determined with regard to a reference anatomic structure.
- 9. Stent Fracture at 30 days, 12-, 24- and 36 months:**  
Fracture or breakage of any portion of the stent.  
Determined by X-ray for the first 30 subjects at 30 days and for all subjects (including the first 30 subjects) at 12-, 24- and 36 months using the following classifications (36) as adjudicated by a venous stent fracture core laboratory:
  - i. Type 0 – No strut fractures
  - ii. Type I – Single tine fracture
  - iii. Type II – Multiple tine fractures
  - iv. Type III – Stent fracture(s) with preserved alignment of the components
  - v. Type IV – Stent fracture(s) with mal-alignment of the components
  - vi. Type V – Stent fracture(s) in a trans-axial spiral configuration
- 10. Change in VEINES-QOL/Sym Score at 6-, 12-, 24- and 36 months:** Defined as the change in VEINES-QOL/Sym score at 6, 12, 24, and 36 months compared to baseline.
- 11. Change in VILLALTA Score at 6-, 12-,24-, and 36 months:** Defined as the change in VILLALTA score at 6, 12, 24, and 36 months compared to baseline.
- 12. Change in EQ5D Quality of life Score at 6-, 12-, 24-, and 36 months:** Defined as the change in Quality of Life Score as assessed by EQ5D questionnaire at 6, 12, 24, and 36 months compared to baseline.

- 13. Change in VCSS Score at 6-, 12-, 24-, and 36 months:** Defined as the change in VCSS Score at 6, 12, 24, and 36 months compared to baseline.
- 14. Major bleeding complication at 30 days, 6-, 12-, 24- and 36 months:** A blood loss leading to transfusion of whole blood or red cells provided hemoglobin drop of 3 g/dL (1.86 mmol/L) or more is related to bleeding occurring during the index procedure through 36 months post-index procedure.
- 15. Medical resource utilization through 36 months** including length of stay and re-hospitalizations.

### **Secondary Endpoint Analysis Method**

Secondary Endpoint	Endpoint Category
1. Device success	Clinical/Safety Endpoint
2. Lesion success	Core Laboratory Endpoint
3. Procedure success	Clinical/Safety Endpoint
4. Primary Assisted Patency at 12 months	Imaging + Clinical/Safety Endpoint
5. Secondary Patency at 12 months	Imaging + Clinical/Safety Endpoint
6. Target Lesion Revascularization (TLR) through 30 days, 6-, 12-, 24- and 36 months	Clinical/Safety Endpoint
7. Major Adverse Events (MAE) through 6-, 12-, 24- and 36 months	Clinical/Safety Endpoint
8. Delayed Stent Migration at 12-, 24- and 36 months	Imaging Endpoint
9. Stent Fracture at 30 days, 12-, 24- and 36 months	Imaging Endpoint
10. Change in VEINES-QOL/Sym Score at 6-, 12-, 24- and 36 months	Endpoint Assessed by Clinic Visit
11. Change in VILLALTA Score at 6-, 12-, ,24-, and 36 months	Endpoint Assessed by Clinic Visit
12. Change in EQ5D Quality of life Score at 6-, 12-, 24-, and 36 months	Endpoint Assessed by Clinic Visit
13. Change in VCSS Score at 6-, 12-, 24-, and 36 months	Endpoint Assessed by Clinic Visit
14. Major bleeding complication at 30 days, 6-, 12-, 24- and 36 months	Clinical/Safety Endpoint
15. Medical resource utilization through 36 months including length of stay and re-hospitalizations.	Clinical/Safety Endpoint

## **7.10 Safety Evaluation**

For adverse events (AEs), serious adverse events (SAEs), major adverse events (MAE) and Unanticipated Adverse Device Effects (UADEs) reporting, the primary analysis will be based on subject counts, not event counts. The subject counts and the percentages will be presented in tabular summaries of results. Reporting of laboratory finding will be reported descriptively.

## **7.11 Health Outcomes Analyses**

VEINES-QOL/Sym score, VILLALTA score, VCSS and EQ5D Quality of Life score change from baseline to 6,12, 24, and 36 months will be reported for this study.

## 7.12 Changes to Planned Analysis

Any changes to the analysis plan will be documented in Clinical Study Report with the reason for the change.

## 8. Validation Requirements

---

Statistical analysis will be validated using double programming for all study endpoints.

## 9. References

---

There were no references needed for this SAP.

## 10. Statistical Appendices

---

### Appendix A – Data Handling and Analysis Incomplete Data

If a date needed for calculation is an incomplete date (e.g. \*\*112006 or \*\*\*\*2006) it will be completed as follows:

For incomplete event dates '01' or '0101' will be entered, respectively (worst case).

However, if an imputed event date is before date of procedure, the date of event will be set equal to the date of procedure.

For all other incomplete dates '15' or '01JUL' will be entered, respectively (less far from correct date). If the missing month is known to be between July and December, the month September will be used.

If the entire start date of an event is missing the index procedure date will be imputed.

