**Table 6: Schedule of Assessments and Visit Windows**

Data Collection Requirement	Screening/Baseline ( $<30$ days before procedure unless otherwise specified)	Procedure	Hospital Discharge	30 Day (-7/+14 days)	6 Months ( $\pm 30$ days)	12 Months ( $\pm 30$ days)	24 & 36 Months ( $\pm 30$ days)	Unscheduled visit for intervention in target vein
Informed Consent	X							
Demographics, Medical History & Physical Examination	X							
Pregnancy Test 	X							
CEAP Classification	X							
Physical Assessment of Limbs	X		X	X	X	X	X	X
Villalta Score, VCSS	X			X	X	X	X	X 
VEINES-QOL/Sym, EQ-5D QOL	X				X	X	X	X 
Procedure Data		X						X
Serum Creatinine, CBC	X							
INR (if on warfarin)	X			X	X	X	X	X
Document Adverse Events	X 	X	X	X	X	X	X	X
Document Device Deficiencies		X	X	X	X	X	X	X
Medication 	X	X	X	X	X	X	X	X
Discontinuation Information 			X	X	X	X	X	X

 Pregnancy test for women of child-bearing potential only. Must be done within 7 days prior to the index procedure.

 Adverse Event assessment need to be done as of the moment the subject is enrolled in the study (i.e. subject signed and dated the informed consent form).

 Medication which will be collected: Antithrombotics, Antibiotics, Immunosuppressants, NSAIDs, Steroids, Diuretics, Calcium-channel blockers, Statins

 Assessments and questionnaires should be taken before any intervention.

 The discontinuation data is needed whenever the subject ends involvement in the study.

**Note:** Only approved devices and therapies may be used during the entire study duration.

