## 10.2 General Analysis Definitions

Assessments will be presented chronologically by study day, which is defined in the following:

Study day = assessment day – date of index-procedure.

Index-procedure day = 0. Events occurring on the day of the index-procedure will be considered day 0.

Note: if the staged procedure is 14 days post index-procedure and an event occurs on this day this event will be reported on day 14 even if it is clearly attributed to the staged procedure.

Events occurring on the day of discharge will be considered in-hospital.

Time of follow-up = date of last contact – date of index procedure. where date of last contact includes but not limited to date of death or the latest of: (1) date of last adverse event, (2) date of last image, (3) date of last procedure, (4) date of last scheduled or unscheduled -follow-up visit, (5) date of Study Exit.

Events will be reported up to the number of months times 30. So, for 6 months  $6 \times 30 = 180$  days will be used, and for 12 months or 1 year, 360 days will be used. For analysis at each time point, subjects will be censored at the time point or time to follow-up as defined above, whichever is earlier.

For all the clinical/safety endpoints, the denominator will include subjects who either have an adjudicated event (e.g. death, revascularization) before the time of interest, or have a contact beyond the lower window of the follow-up.

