1. CD-TLR
2. Imaging endpoint of Occlusion/Restenosis

Primary patency endpoint determination will follow the rules described below:

1. Censor any imaging assessments or events after any TVR (not clinically driven) as this changes the vessel making the subject unevaluable for patency at 12 months. If the date of assessment > date of TVR, then set the value to 'missing'
2. All Subjects that had CD-TLRs within 390 days will be counted as Primary Patency Failure whether or not an imaging assessment is available after the CD-TLR event. Subjects with TVR (not clinically driven) before the CD-TLR will be censored.
3. The imaging component of the 12-month primary patency will be constructed based on 'AT' principle – prior events will not be carried over to a later visit. For each subject, qualified imaging assessment will be determined in the following order:
  - a. Venogram on scheduled 12-month visit regardless of window.
  - b. DUS on scheduled 12-month visit regardless of window
  - c. Venogram from unscheduled visit within the imaging window, choose the one closest to the target visit date if there are multiple
  - d. DUS on unscheduled visit within the imaging window, choose the one closest to the target visit date if there are multiple

Primary Patency at 24 months, and 36 months follow-up will be determined following the similar convention specified above for 12 months.

For each individual component of the primary patency endpoint, the rate will be calculated in the following way:

The proportion rate of CD-TLR will be constructed as a clinical/safety endpoint - number of subjects with CD-TLR over number of evaluable subjects through the cutoff of a reporting time point. For example, for 12-month CD-TLR under the primary patency endpoint, the cutoff to determine the numerator is 390 days – this includes any subjects who had their first CD-TLR within 390 days. The denominator will be all subjects that had CD-TLR or had no CD-TLR but had at least 330 days of clinical follow-up.

The CD-TLR Endpoint will be reported cumulatively.

The determination of imaging component of the occlusion/restenosis endpoint is described above.

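### The earliest-date rule for incomplete event dates is not worst case for a re-intervention that is not clinically driven: it can turn a 12-month patency failure into a missing value

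*SAP*

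**What the plan says.** SAP Appendix A (Incomplete Data) handles incomplete event dates in three steps.

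- A missing day becomes the 1st, and a missing day and month become 1 January: "For incomplete event dates '01' or '0101' will be entered, respectively (worst case".
- The only floor is the index procedure: "if an imputed event date is before date of procedure, the date of event will be set equal to the date of procedure".
- A wholly missing date becomes day 0: "If the entire start date of an event is missing the index procedure date will be imputed".

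SAP 10.2 treats a revascularization as an event, since its denominator counts "subjects who either have an adjudicated event (e.g. death, revascularization) before the time of interest". The date rule therefore reaches re-interventions.

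SAP 10.3.2.2, rule 1, then applies to re-interventions that are not clinically driven: "Censor any imaging assessments or events after any TVR (not clinically driven) as this changes the vessel making the subject unevaluable for patency at 12" (that is, at the 12-month assessment). The test is strict: "If the date of assessment > date of TVR, then set the value to 'missing". Rule 2 makes every clinically driven TLR within 390 days a Failure whatever the imaging, but censors the subject if a TVR that is not clinically driven came first.

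SAP 7.9.1.2 allows an image taken on or before the TVR date, within the 12-month window, still to be used. SAP Table 5 scores a failing 12-month image as Failure, but gives Missing when a TLR that is not clinically driven precedes 12 months, any clinically driven TLR and the 12-month image. The primary patency rate is computed among evaluable subjects only.

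**The concern.** The early date is the cautious choice only when the event counts against the device. A re-intervention that is not clinically driven does not count against it in the primary endpoint; it removes later evidence. For that event type the earliest date removes the most evidence, so the worst-case label is wrong.

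The sequence is foreseeable. Protocol 10.9 calls for a venogram when the 12-month duplex scan suggests at least 50% restenosis. If the subject has no symptoms and is then re-treated, the re-treatment falls outside the protocol's definition of clinically driven, and it follows the failing image. If its day is not recorded, the imputed date can jump ahead of that image.

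At stake is a core-laboratory failure leaving the denominator of a pass/fail endpoint because of an imputed date. The error favours meeting the 75% goal. Nothing in the SAP checks the imputed date against documented images or procedures.

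**Working it through.** **1. The plan's own figure.** SAP 6.3 gives N = 160, P0 = 0.75, P1 = 0.857, reject if R ≥ 131, alpha 0.0247, power 0.9288. Exact binomial: P(X ≥ 131 | 160, 0.75) = 0.0247 and P(X ≥ 131 | 160, 0.857) = 0.9288. Both reproduce.

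**2. The rules applied to one subject (dates assumed).** Index procedure 5 March 2018; failing 12-month image 8 March 2019 (day 368); TVR, not clinically driven, 25 March 2019 (day 385).

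| TVR date available | Date used | Study day | Image after TVR? | Result |
|---|---|---|---|---|
| Full | 25 Mar 2019 | 385 | No | Failure |
| Day missing | 1 Mar 2019 | 361 | Yes | Missing |
| Day and month missing | 1 Jan 2019 | 302 | Yes | Missing |
| Wholly missing | 5 Mar 2018 | 0 | Yes | Missing |

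In the day-missing row the imputed day is just past 360, so rule 1 does the work alone; in the last two rows Table 5 gives Missing as well.

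**3. How often the image would be lost, given an incomplete date.** With only the day missing, the image is lost when it falls in the same calendar month as the re-treatment and after the 1st. With image dates spread evenly over one year (assumed):

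- Fixed lag from image to re-treatment of 1, 7, 14, 21 or 30 days: 93%, 74%, 51%, 28%, 0%.
- Lag uniform on 1–14, 1–30 or 1–60 days: 72%, 46%, 23%.
- Day and month missing, lag 7, 30 or 90 days: 98%, 92%, 75%.

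**4. Effect on the test.** The lower limit is the 0.025 quantile of Beta(x, n − x + 1). SAP 7.9.1.2 does not name the interval method for patency; I use the exact one to match the sample-size calculation.

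| Patent / evaluable | Rate | One-sided 97.5% lower limit | Goal of 75% |
|---|---|---|---|
| 131/161 | 81.4% | 74.5% | missed |
| 131/160 (one failure removed) | 81.9% | 75.02% | met |
| 130/160 | 81.3% | 74.3% | missed |
| 130/159 (one removed) | 81.8% | 74.9% | missed |
| 130/158 (two removed) | 82.3% | 75.4% | met |

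Across evaluable sizes 160 to 200, removing one failure from a result one success short of the pass line gives a pass at 32 of 41 sizes. The design size of 160 is one of the nine exceptions. At a true rate of 85.7%, the chance of landing exactly one success short is 1.1% to 3.0%, depending on the size.

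**The case against.** The strongest objection is that a re-intervention without a recoverable date should be rare. Protocol 10.11 requires imaging and secondary procedure data at any target-vein intervention. Protocol 12.2.1 collects the date of intervention and lets the diagnosis date stand in for an incomplete onset date. Target limb revascularizations go to the CEC (Protocol 14.4.2). Protocol 16.6 states 100% source verification up to the primary endpoints. The definition of clinically driven is also broad, so few re-treatments will fall outside it. All of this stands and limits the size of the problem, but none of it changes the rule.

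The tipping-point analysis (SAP 7.4.2) would partly expose the effect. Multiple imputation (SAP 7.4.1) would not: it would replace a known failure with a model draw.

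Some wider readings are tempting but not supported.

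- **All re-interventions are affected.** No. A clinically driven TLR within 390 days is a Failure whatever the imaging, and an early date for it is conservative.
- **A back-dated death removes patency failures.** SAP 10.2 words last contact as "where date of last contact includes but not limited to date of death or the latest of" several dates, but SAP 10.3.1 bases it on all available follow-up dates. A failing core-laboratory image is in any case evaluable without the 330-day minimum, so only event-free subjects could be lost.
- **Year-only events inflate the 30-day safety endpoint.** They may, but this counts against the device, as the label says.
- **Adverse events between consent and procedure move to day 0.** They may, since Protocol Table 6 says "Adverse Event assessment need to be done as of the moment the subject is enrolled in the study". The MAE components are post-procedural or stent-related and are adjudicated or confirmed by the core laboratory, so this is mainly a tabulation matter.
- **The subject becomes a success.** One could argue this from evaluability item (c), 330 days without an event. Table 5 assigns Missing to a TLR dated before the image, and I follow it.

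**Conclusion.** The gap is real and narrow. It needs a TVR/TLR that is not clinically driven, an incomplete date for it, and a failing 12-month image (or a clinically driven TLR) that came before it but after the imputed date. Where all three hold, the plan turns a documented failure into a missing or censored outcome, in the direction that favours the device.

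The documents do not give the number of such dates, and the data-collection safeguards suggest it is very small. One subject could change the conclusion only within a success or so of the pass line; at 160 evaluable subjects it takes two. The percentages for losing the image are conditional on an incomplete date and on assumed lags, so they are not estimates of how often this occurred.

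SAP 10.3.2.2 extends a similar convention to primary patency at 24 and 36 months. There monitoring is risk-based and missed visits may be covered by telephone (Protocol 16.6 and 10.10), so incomplete dates are more plausible, though that endpoint is descriptive. The correction is worth making because it is specific and nearly free.

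**What to change.** Add to SAP Appendix A, for a TVR/TLR that is not clinically driven and has an incomplete date:

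1. The imputed date must not precede any image or clinically driven TLR that procedure data, CEC or core-laboratory records show came before the re-treatment. A failing image known to precede it stays a Failure.
2. Images known to follow the re-treatment remain set to missing under rule 1 of 10.3.2.2.
3. Where the order is unknown, a failing image within the 12-month window counts as Failure and a patent image is set to missing.

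Keep the first-of-month rule for all other events. A blanket latest-possible date would be a poor substitute: a patent scan taken after the re-treatment could then count as Success.

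The cost is three sentences and a small change to the date-derivation program, with no new data. Because the 12-month data have already supported the PMA, also list any re-interventions of this type whose dates were imputed in that analysis. If there are none, one line in the report closes the point for the primary endpoint.
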